6. TRIAL DESIGN

The OxAMI-PICSO study is a prospective single centre observational cohort study of the use of PICSO in patients presenting for primary PCI for acute myocardial infarction. The OxAMI- PICSO study is based upon the established framework of the OxAMI study (Ethics Ref 11/SC/0397).

Patients, age 30-90, presenting with ST elevation myocardial infarction will be considered for inclusion in the study. Measurement of IMR before stenting is an essential prerequisite for the study: only patients with pre-stenting IMR > 40 will be considered eligible for the PICSO treatment. Patients with IMR≤ 40 will remain in the study but will not undergo PICSO treatment. The procedure for consent in patients undergoing emergency PCI will be as already established in the ongoing OxAMI study, and is discussed below in Section 8.1.2.

The PCI procedure will be undertaken in a standard fashion, and include the use of pressure wire measurements before and after stent deployment. Aspiration or distal protection devices may be used if clinically indicated and where vessel anatomy is suitable. The devices used and the procedural techniques will be driven by clinical decision making at the patient and institutional level, and carried out in accordance with the Oxford University Hospitals NHS Trust (OUHT) departmental guidelines for PCI.

PICSO treatment will be added on top of the conventional treatment.

The protocol will constitute of 5 main stages described in details in the next sections (Section 8.3).

Only patients with pre-stenting IMR > 40 and who assent to receive PICSO treatment will undergo 24 hours coronary angiogram with coronary physiology measurement, 24-48 hours CMR scan and 6 months CMR scan. Patients who assent to participate in the study but in whom the pre-stenting IMR ≤ 40, or those in whom the pre-stenting IMR > 40 but the participant declines PICSO treatment will remain in the study for blood sampling and clinical data collection at the same follow up time points (24 hours, 48 hours and 6 months). A summary of the study design, indicating the time points and procedures, is shown in Section 8.3.

7. PARTICIPANT IDENTIFICATION

7.1. Trial Participants

Participants aged 30-90 years old, referred for emergency diagnostic coronary angiography presenting with ST elevation myocardial infarction, with the intention to proceed to primary PCI with stenting.

7.2. Inclusion Criteria

Participants must satisfy the following conditions:

- Male or Female, aged 30 to 90 years,
- Clinical presentation with STEMI
- Referred for coronary angiography with view to proceed to PCI with stenting.

7.3. Exclusion Criteria

The participant may not enter the study if ANY of the following are known to apply:

- Patients in whom safety or clinical concerns preclude participation.
- Known anaemia (Hb <9).
- Pregnant or breast feeding females.
- Revascularization by mean of balloon angioplasty without stenting
- History of stroke, TIA or reversible ischemic neurological disease within last 6 months
- Known severe renal failure (eGFR < 30 ml/min/1.73m²) or history of dialysis or renal transplant
- Previous coronary bypass artery grafting
- Known severe valvular abnormalities
- Previous STEMI presentation
- Presentation with cardiogenic shock
- Severe bradycardia (Heart rate < 50 beats per minutes)
- STEMI due to stent thrombosis
- Unconscious on presentation

- Non-cardiac comorbidities and life expectancy < 1 year
- Use of warfarin
- Presence of pacemaker or other electrodes in the coronary sinus
- Contraindications to adenosine
- Additional exclusion criteria for participants undergoing CMR
 - claustrophobia which limits / prevents participants from remaining in CMR scanner.
 - patients who cannot lie flat on the scan table.
 - patients with metallic implants, pacemakers, implantable defibrillators etc, unless known to be CMR compatible.
 - patients with known allergy to medium of contrast (gadolinium)

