8.3.1 Stage 1: Pre-Stenting

- Diagnostic angiography will be performed in the standard manner using appropriate catheters.
- Bivalirudin will be administered (0.75mg/kg bolus followed by an infusion of 1.75 mg/kg/min for up 4 hours after the procedure as clinically warranted), as routinely used for PCI. The lesion will be

crossed with a coronary guide wire in the usual manner for PCI. Normal blood flow will be rapidly achieved by thrombus aspiration and/or predilation

3. Pre-stenting coronary physiology parameters, namely FFR, CFR and IMR, will be measured, using a pressure wire, as used for routine clinical measurements in patients undergoing PCI.
4. If pre-stenting IMR is > 40 , patients will be invited to receive the PICSO device. If pre-stenting IMR is ≤ 40 PICSO device will not be proposed, but the patient will be invited to remain in the study for serial blood sampling (procedural-6 hours-24 hours and 48 hours) and routine clinical data collection.

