8.3.2 Stage 2: PICSO treatment

1. In patients with IMR >40 who assent to PICSO treatment, the PICSO device will be deployed as already previously described in the literature [22] (Section 9.2). The overall duration of PICSO will be no less of 60 minutes up to a maximum of 90 minutes in order to ensure a PICSO delivery dose of 800 mmHg.

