12.2 Analysis of Endpoints

In keeping with our usual practice we will obtain expert statistical advice from the Centre for Statistics in Medicine (or equivalent) for each specific task. Summary statistics, including means, medians, and

variances, will be calculated at each time point and for each type of data (e.g. parameters derived from coronary physiology and CMR). The distribution of the levels will be described. It may be necessary to log transform the data before further statistical analysis. For each parameter an analysis of variance will be carried out at each time point.

Control group in OxAMI-PICSO study is represented by a highly matched group of patients underwent to primary PCI, with a prestenosing IMR > 40 and with available 24 hours recath and 24-48 hours/6 months CMR data. Matching will be performed by application of a propensity score matching analysis including the following predictors in the model: age, sex, pain to wire time, thrombotic burden (assessed as angiographic thrombus score), thrombus aspiration performance, stent volume, glycoprotein IIbIIIa inhibitors adoption.

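### Two rules, the balloon-only exclusion in 7.3 and stent-volume matching in 12.2, turn on stenting, which comes after PICSO starts, so a treated but unstented patient could fall out of the primary comparison

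*Combined protocol and SAP*

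**What the plan says.** All references are to the combined protocol and SAP.

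- **Inclusion (7.2)** goes by intention: "Referred for coronary angiography with view to proceed to PCI with stenting".
- **Exclusion (7.3)** opens with "The participant may not enter the study if ANY of the following are known to apply". One item in that list is "Revascularization by mean of balloon angioplasty without stenting".
- **Device decision (Section 6):** "only patients with pre-stenting IMR > 40 will be considered eligible for the PICSO treatment".
- **Stage order (8.3.1 to 8.3.3).** Flow is restored and IMR is measured in Stage 1. In Stage 2, "In patients with IMR >40 who assent to PICSO treatment, the PICSO device will be deployed". Stenting, by routine practice, is Stage 3. Appendix A likewise puts the start of PICSO before the end of PCI.
- **Matching (12.2).** The propensity model's predictors end with "stent volume, glycoprotein IIbIIIa inhibitors adoption". The section names no analysis population.
- **Follow-up and safety.** Sections 8.3.4 and 8.3.5 tie CMR to receipt of the device. Section 11.3 records all adverse events. Section 11.4 records serious events from assent or device use to 30 days after device use. Section 5 lists rates of deployment failure and coronary sinus complications without stating their denominators.

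**The concern.** The 7.2 criterion can be judged when the patient is referred. The 7.3 item names a completed form of revascularization, and whether a stent was placed is certain only when the procedure ends. For a treated patient that is after PICSO has begun. Stent volume is also fixed in Stage 3, so the matching conditions on something that happens after exposure starts.

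The study is not randomised and staff know who was treated. If whether to keep an unstented, device-exposed patient is decided after the event, the treated group can be shaped by how procedures went. Two results are exposed: the infarct-size comparison at 24-48 hours, and the device safety rates. With about 25 treated patients, one patient or one event moves either of them.

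**Working it through.** The plan has no figure of its own on this point to reproduce. The check is one of sequence, followed by an illustration of scale.

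**When each fact becomes known**

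| Fact | Source | Settled |
|---|---|---|
| Intention to stent | 7.2 | At referral |
| Assent | 8.1.1.1, Appendix A | Before PCI |
| Pre-stenting IMR | 8.3.1 | Stage 1, before PICSO |
| PICSO started | 8.3.2 | Stage 2 |
| Stent placed or not | 8.3.3 | Stage 3, after PICSO starts |
| Stent volume | 8.3.3, used in 12.2 | Stage 3, after PICSO starts |

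The order is deliberate: Section 4.2 counts deployment after stenting among the limitations of the earlier STEMI study. Some balloon-only cases may be recognised in Stage 1, where "Normal blood flow will be rapidly achieved by thrombus aspiration and/or predilation". Those are settled before the device and raise no problem. The gap concerns only patients whose unstented outcome emerges after PICSO has started.

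**What the text does with such a patient**

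- Section 8.2 covers withdrawal and death only.
- Section 8.4 stops recruitment at 25 patients treated and followed to 6 months, and 12.1 aims for 25 with complete data. A dropped patient could be replaced without any record of it in the analysis.
- In the propensity model the patient's stent volume is zero. If the controls were stented, as matching on stent volume suggests, none may be close enough to match. This route does not depend on how 7.3 is read.
- The 6-hour sample (8.3.3) and the treatment time after repositioning (10.2) are counted from stent deployment, which has no value in this patient. The 10.2 clock should also be reconciled with the stage order in 8.3.

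**Scale, on assumed counts.** The documents give no unstented rate.

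- One dropped of 26 treated: 1/26 = 3.8%. Two of 27: 2/27 = 7.4%.
- If one of those two had the only coronary sinus complication, the rate would read 0/25 = 0% instead of 1/27 = 3.7%; Section 10.2 cites under 3%. The exact 95% intervals, about 0-14% and 0.1-19%, overlap widely.

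**Infarct size, on assumed inputs.** Let a share e of treated patients be dropped, with infarcts larger than those of retained patients by a fraction d. Assume no true effect and no corresponding exclusion among controls. Set the mean of all treated patients to 1, equal to controls. The retained mean is then 1/(1 + e·d), and the apparent reduction is 1 − 1/(1 + e·d).

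| e | Treated needed for 25 retained, 25/(1 − e) rounded up | d = +0.5 | d = −0.5 |
|---|---|---|---|
| 5% | 27 | 2.4% | −2.6% |
| 10% | 28 | 4.8% | −5.3% |
| 20% | 32 | 9.1% | −11.1% |

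For example, 1 − 1/(1 + 0.10 × 0.5) = 1 − 1/1.05 = 4.8%. The planned effect in 12.1 is a 29% reduction. The sign follows d, about which the documents say nothing.

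**The case against.** The strongest answer is the opening sentence of 7.3. It limits the list to entry and to what is known. A patient who ends unstented after PICSO has already entered, and the fact was not known at entry. Follow-up, the recruitment stop and adverse-event recording all go by the device, with no stent condition. All of this stands, and it rules out several stronger readings that a reader might infer:

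- **That the protocol requires treated, unstented patients to be removed.** No section says so.
- **That their complications would go unrecorded.** Sections 11.3 and 11.4 capture them. Only the denominators of the reported rates are undefined.
- **That controls are chosen under a looser rule.** Section 12.2 requires a pre-stenting IMR above 40, a 24-hour repeat catheterisation and CMR data. Section 5 says controls followed the rest of the study protocol, and matching on stent volume suggests that they were stented. The rule for controls is unstated rather than shown to differ.
- **That the result is flattered.** The direction cannot be derived from the documents.

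It may also be said that stent volume is a separate matter. It does stand on its own, but it belongs here because it can put the same patient outside the same comparison. What the objection does not answer is that 7.3 names a treatment performed, that 7.2 already covers intention, and that 12.2 has no analysis population to prevent later use of the item.

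**Conclusion.** The point holds as a gap that leaves room for selection after exposure, not as a rule that commands it. There are two routes: the 7.3 item applied once the procedure is over, and matching on a variable fixed after PICSO starts. The second is explicit in 12.2 and is the firmer of the two. The sequence rests on the text alone. Every count and percentage above rests on assumed numbers of unstented patients and assumed infarct sizes, so neither the size nor the direction of any bias is known. The change is worth making because the treated group is small, the comparison is not randomised, and the remedy is confined to wording and analysis.

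**What to change.** 1. In 7.3, state that the balloon-only item is judged solely on facts known before PICSO is offered.
2. In 12.2, define the primary comparison and the denominators for deployment failure and coronary sinus complications as all patients in whom PICSO placement was attempted, whether or not a stent followed. The primary comparison uses those with CMR data: Section 6 ties CMR to assent, but 8.3.4 and 8.3.5 tie it to receipt of the device, so some failed placements may lack it. Report the number of unstented patients and their outcomes.
3. Apply the same pre-stenting rule when selecting OxAMI controls.
4. Replace stent volume in the propensity model with lesion or vessel measures taken before PICSO. Keep stent volume for a sensitivity analysis at most.

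The cost is slight heterogeneity from a few unstented patients and some loss of a lesion-size proxy. The work is wording in 7.3 and 12.2, plus extracting pre-PICSO lesion measures for both groups.

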8. TRIAL PROCEDURES

8.1. Informed Consent

Informed consent will be obtained, with the recruitment approach to the patient, as described below.

8.1.1 Patients proceeding to emergency angiogram/PCI

The clinical treatment of these patients is in the emergency context and delays to treatment are detrimental. It is necessary to administer prompt emergency treatment and it is not always possible to identify and approach a Consultee beforehand. Thus we would seek a waiver, as described in Section 32(9) of the Mental Capacity Act, since

- a) the treatment needs to be given urgently,**
- b) it is necessary to take the action for the purpose of the research urgently,**
but
- c) it is not reasonably practicable to consult prior to enrolling the patient.**

In this situation the Mental Capacity Act allows the participant to be enrolled with a agreement of a registered medical practitioner (RMP) not involved in the research or in accordance with a procedure agreed with the appropriate body (i.e. REC). Since this is only applicable for the duration of the emergency we will seek written informed consent as soon as reasonably practicable (see diagram and Section 8.1.1.2 below). This process includes an important role for a healthcare professional as a type of patient “advocate”. This is discussed in section 8.1.1.2 below. We also seek approval from the REC for the waiver procedure.

8.1.1.1 Verbal assent

Because of the urgency of the situation it is not feasible to obtain fully informed written consent. Fully informed consent requires that the potential participant have time to read and reflect on a patient information sheet which in this context is clinically inadvisable. We therefore propose to obtain verbal assent so as to optimize the amount of appropriate information conveyed to potential participants acutely and minimize the clinical risks involved with substantial delay. The research study will be discussed verbally with the patient and the risks and benefits explained.

In detail the patient at the time of verbal assent process will be informed that as part of the research project he might undergo to some extra blood samples and to measurement of the index of microcirculatory resistance (IMR) which allows to have an indirect assessment of the entity of the ongoing heart attack. The patient will be also informed that in case IMR value will be greater than 40, thus suggesting a possible significant damage to the heart muscle that may benefit from additional treatment, he might be asked to provide assent for PICSO treatment. Patients with pre-stenting IMR \leq 40 or those with pre-stenting IMR $>$ 40 who elect not to receive PICSO treatment will be given the opportunity to continue to participate within the OxAMI-PICSO study, but without the use of the PICSO device.

[figure not shown]
Participants will be reminded that they have the right to withdraw from the study at any stage and that this will not affect their treatment or human rights. The research and clinical team have extensive experience of patient assent, and the role of a Patient Advocate (see below), through the recruitment of approximately 250 participants undergoing emergency PCI for STEMI in the OxAMI study.

Only conscious patients, able to provide verbal assent will be enrolled in the study.

8.1.1.2 Patient Advocate

Because of the urgency of the situation it is not feasible to consult prior to enrolment, a RMP or patient “advocate” will be identified to act in accordance with 32(9). The Patient Advocate will act as witness and documenter of the verbal consent process for all conscious potential participants and/or overseer of the waiver process (8.1.2.3) as a whole. This RMP will be present at the time of emergency treatment, but is not part of the research team. The Advocate will ensure that the verbal consent process is undertaken, that the patient does not object (i.e. the patient “assents” rather than “dissents”), and that the researcher has taken practical steps to explain the study, risks and benefits, within the context of the emergency clinical situation, and in accordance with the clinical status of the patient. The Advocate in this situation will be a healthcare professional such as a specialist nurse. Assessment of patients in this context is within their professional capacity and the role here will be to witness verbal consent or assent.

Most of the nursing staff attended a series of seminars to make them aware of their specific roles and responsibilities in this situation, and they have acted as patients’ advocates through the recruitment of approximately 250 participants undergoing emergency PCI for STEMI in the ongoing OxAMI study. These seminars have been directed by an ethicist who is not directly involved with the research project. We will continue to provide this training and draw on the extensive experience of the members of the clinical team currently acting as a Patient Advocate.

8.1.1.3 Post-emergency phase

Once the emergency phase is over and treatment has been delivered, we will seek full written informed consent as soon as practical. For most patients this means within 12 hours of admission. This consent will be a two parts process:

- a) We will seek consent to allow use of data and samples already acquired during the emergency phase
- b) We will seek consent for ongoing participation in the study.

If the participant elects to withdraw from the study at this point then we will seek consent to use the data and samples already acquired. If this is not given, then all research data and samples acquired during the emergency treatment will be destroyed, otherwise only data acquired in the emergency situation will be retained in the study.

If a patient is unable to provide informed consent at this stage due to deterioration in clinical condition, we propose to keep the data and samples acquired under the assent phase. We would not seek further ‘consent’ from relatives at the risk of causing undue distress.

8.2. Discontinuation/Withdrawal of Participants from Trial Treatment

8.2.1 Study Withdrawal

[figure not shown]
We anticipate and have made provision for withdrawal when the emergency exception period is complete; if a patient is assessed and has capacity then they may completely or partially withdraw at any time. This possibility will be made clear as a part of seeking of full written informed consent after the initial emergency procedure.

8.2.2 Participant death:

If the participant dies before giving full written consent then we propose to continue using the data and samples obtained. We would not seek further ‘consent’ from relatives at the risk of causing undue distress.

8.3 Study timeline (see “Integrated flowchart for OxAMI-PICSO study” as below)

The OxAMI-PICSO study will take place beside an ongoing large prospective observational study in STEMI patients (OxAMI study). Patients fulfilling the OxAMI-PICSO criteria will be invited to participate in the study. OxAMI-PICSO study will constitute of 5 main stages:

8.3.1 Stage 1: Pre-Stenting

- Diagnostic angiography will be performed in the standard manner using appropriate catheters.
- Bivalirudin will be administered (0.75mg/kg bolus followed by an infusion of 1.75 mg/kg/min for up 4 hours after the procedure as clinically warranted), as routinely used for PCI. The lesion will be

crossed with a coronary guide wire in the usual manner for PCI. Normal blood flow will be rapidly achieved by thrombus aspiration and/or predilation

3. Pre-stenting coronary physiology parameters, namely FFR, CFR and IMR, will be measured, using a pressure wire, as used for routine clinical measurements in patients undergoing PCI.
4. If pre-stenting IMR is > 40 , patients will be invited to receive the PICSO device. If pre-stenting IMR is ≤ 40 PICSO device will not be proposed, but the patient will be invited to remain in the study for serial blood sampling (procedural-6 hours-24 hours and 48 hours) and routine clinical data collection.

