9.4 Analysis of cardiac physiological measurements

Cardiac and/or coronary flow and pressures will be measured, before and after stenting and during the repeat coronary angiogram at 24 hours post-PPCI, using commercially available measurement guidewires

according to standard techniques that are in routine use in current PCI practice. The guidewire contains a pressure-temperature sensor to allow for calculation of the physiological parameters. The guide wire is calibrated at the beginning of the PCI and then advanced into the distal third of the culprit artery. Calculations will be based on measurements of proximal and distal coronary pressure(s) and mean transit time (in seconds) during maximal hyperemia, as previously described. Briefly a pressure wire (Radi; St Jude Medical, St Paul, MN, USA) is placed in the LAD distal to the lesion. Baseline mean aortic pressure (Pa), mean distal pressure (Pd) and Pd/Pa ratio will be recorded. Thermodilution-based measurement of CFR and IMR will be performed by injecting in the IRA 5 ml of room temperature saline solution and recording mean transit time (meanTt) at baseline and after induction of maximal hyperaemia by intravenous infusion at a rate of at a rate of 140 mg/kg/min. Once hyperaemia is achieved the following parameters will be obtained: FFR (Pd/Pa during hyperemia), CFR (meanTtbaseline/meanTthyperaemia) and IMR (Pdhyperaemia* meanTthyperaemia).

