16.2 Possible risks and/or discomfort for patient

Patients referred for cardiac catheterization and PCI will undergo this procedure as would routinely be performed. Patients will therefore be consented for the standard of care procedure and its associated risks.

Overall the PCI procedure time may be lengthened by around 20 minutes to complete the selected study procedures (cardiac physiological measurements + PICSO catheter placement). In the context of a PCI procedure that typically last approximately 60 minutes; the additional time taken should not result in any clinically significant difference to the participants. Very occasionally this additional time can result in some back discomfort for patients having to lie on the angiography bed for the additional time period.

CMR is an established cardiac imaging technique in our institution and is generally very well tolerated. Specific considerations for safety are reflected by the additional exclusion criteria listed in section 7.3. All local protocols will be adhered to and only fully trained staff will carry out procedure according to departmental SOPs.

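### Section 8.3.1 prints the bivalirudin infusion as 1.75 mg/kg per minute; the time unit is very probably wrong and should be verified and corrected

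*Combined protocol and SAP*

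**What the plan says.** Item 2 of Section 8.3.1 (Stage 1: Pre-Stenting) specifies bivalirudin as "0.75mg/kg bolus followed by an infusion of 1.75 mg/kg/min for up 4 hours after the procedure". The duration is qualified by "as clinically warranted), as routinely used for PCI". The step comes before item 4, where participants are divided by IMR, so it covers those who receive the device and those who do not.

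This is the only place where the documents give a bivalirudin dose. No other section states a second rate, a maximum dose or a correction.

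Section 16.2 gives the durations needed to size the problem. It describes the usual procedure with the words "In the context of a PCI procedure that typically last approximately 60 minutes", and says of the study steps: "Overall the PCI procedure time may be lengthened by around 20 minutes to complete the selected study procedures".

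**The concern.** A bolus given ahead of an infusion normally serves as a loading dose, with the infusion maintaining the effect. At the printed rate the infusion overtakes the bolus almost at once, which does not fit a regimen described as routine. The likeliest explanation is that the time unit was mistyped. This is an implausible single figure, not a contradiction between two stated figures.

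The drug is an anticoagulant and the text is a dosing instruction for an emergency procedure. Section 10.2 lists bleeding from coronary sinus damage and from femoral vein access among the device risks, and reports one tamponade after coronary sinus perforation in earlier human studies. Section 5 makes coronary sinus perforation a tertiary outcome. Section 14 says the trial will follow the approved protocol and that monitors will check compliance with it. Staff who give a different rate therefore depart from the written protocol, and staff who follow it give 60 times the per-hour dose.

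**Working it through.** **Inputs**

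- Bolus: 0.75 mg/kg (Section 8.3.1).
- Infusion rate as printed: 1.75 mg/kg/min (Section 8.3.1).
- Post-procedure infusion: up to 4 hours, or 240 minutes (Section 8.3.1).
- Procedure length: about 60 minutes, or 60 + 20 = 80 minutes with the study steps (Section 16.2).
- Assumption: the infusion starts straight after the bolus and runs through the procedure.

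**Formulas.** Cumulative infusion dose = rate × time. Multiple of bolus = cumulative dose / 0.75. Time to repeat the bolus = 0.75 / rate.

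**Time to repeat the bolus.** 0.75 / 1.75 = 0.4286. As printed, this is 0.4286 minutes, or 25.7 seconds. If the unit were per hour, it would be 0.4286 hours, or 25.7 minutes.

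**Cumulative dose**

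| Infusion time | Per minute, as printed | Multiple of bolus | Per hour, assumed | Multiple of bolus |
|---|---|---|---|---|
| 60 min (procedure only) | 1.75 × 60 = 105 mg/kg | 140 | 1.75 mg/kg | 2.3 |
| 80 min (procedure and study steps) | 1.75 × 80 = 140 mg/kg | 187 | 2.33 mg/kg | 3.1 |
| 240 min (4 hours only) | 1.75 × 240 = 420 mg/kg | 560 | 7.0 mg/kg | 9.3 |
| 320 min (80 min and 4 hours) | 1.75 × 320 = 560 mg/kg | 747 | 9.33 mg/kg | 12.4 |

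The two readings differ by 420 / 7.0 = 60. The printed rate delivers the whole 4-hour per-hour total in 7.0 / 1.75 = 4 minutes.

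**Could the mass unit be wrong instead?** At 1.75 microgram/kg/min, 240 minutes gives 1.75 × 240 / 1000 = 0.42 mg/kg, which is 0.42 / 0.75 = 0.56 times the bolus. Four hours of infusion would then give less than the bolus alone. Of the three readings, per hour makes the most coherent loading-plus-maintenance regimen.

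**Scale in one patient.** Body weight is not in the documents. For an assumed 60 to 100 kg, the bolus is 45 to 75 mg. Four hours at the printed rate is 25.2 to 42.0 g; four hours at the per-hour rate is 420 to 700 mg.

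**The case against.** The strongest objection is that nobody would give this dose. Bivalirudin is background medication, the sentence itself says "as routinely used for PCI", and Section 6 places the devices and techniques of PCI under the trust's departmental guidelines. Local practice would probably govern, and this is a good reason not to rate the point higher. It does not remove it: Section 6 does not mention drug doses, and neither section corrects the printed figure.

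A second objection is that the duration is left to clinical judgement. That judgement can shorten the post-procedure infusion but does not change the rate. Even with no infusion after a 60-minute procedure, the total is 140 times the bolus.

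A third is that the documents give no pharmacokinetics, no maximum dose and no description of the routine regimen, so they cannot prove which unit was meant. The factor of 60 follows simply from exchanging minutes for hours; it measures the assumed correction and is not evidence for it. This stands as a limit on the claim. The evidence is the ratio of bolus to infusion in a single sentence, which is enough to require a check. The replacement unit has to come from the clinical team.

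Finally, Section 9.4 prints the hyperaemia infusion "at a rate of 140 mg/kg/min". That rate deserves the same check, but it is a separate matter and has no bearing on this one.

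**Conclusion.** The concern holds. The printed rate matches the bolus every 25.7 seconds. It gives 105 to 140 mg/kg over the procedure alone and 420 mg/kg over 4 hours, or 140 to 187 and 560 times the bolus. It is very probably a unit error in a dosing instruction that applies to every participant.

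Confidence is high that the printed unit needs checking. That per hour was intended is an assumption: it fits better than the printed unit or a change of mass unit, but the documents do not state it. The procedure-only figures also assume that the infusion begins right after the bolus. The point should be fixed. Likely reliance on local practice lowers the practical risk, and no statistical feature of the plan is affected.

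**What to change.** The sponsor's clinical team should verify the time unit of the bivalirudin infusion in Section 8.3.1 against local PCI dosing practice and correct it. Per hour is the candidate to confirm. A short clarification should go to the catheter laboratory staff at this single centre. It would be sensible to check the infusion rate in Section 9.4 at the same time.

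The cost is a one-line correction and a clarification note. Sample size, endpoints and analysis do not change.
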